3.2. Subject Grouping

For analyses based on the All Randomized and ITT Semen Analysis Sets, subjects will be grouped according to their randomized treatment. For all other analysis sets, subjects will be grouped according to the actual treatment received. The actual treatment received will differ from the randomized treatment only when the actual treatment differs from randomized treatment for the entire treatment duration of the study drug administration period.

The following subject groupings will be applied to the semen and hormone data according to the actual treatment received:

- For the double-blind treatment period, data from subjects who took double-blind treatment will be summarized by treatment group (ie, filgotinib 200 mg and placebo).
- Semen and hormone data collected after Week 13 will be summarized by treatment sequence (ie, double-blind filgotinib, double-blind filgotinib to open-label filgotinib, double-blind placebo, and double-blind placebo to open-label filgotinib) for subjects with baseline and ≥ 1 visit at/after Week 26. Analysis visit windows for the double-blind placebo to open-label filgotinib group will be windowed from the first dose date of open-label filgotinib and will be 13-weeks prior to those who remained on original treatment. All other treatment sequences will have analysis visit windows assigned based on days from first dose of double-blind study drug.

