3.5. Missing Data and Outliers

3.5.1. Missing Data

In general, missing data will not be imputed unless methods for handling missing data are specified. Exceptions are presented in this document.

For missing last dosing date of study drug, imputation rules are described in Section 4.2.1. The handling of missing or incomplete dates for AE onset is described in Section 8.1.5.2, and for prior and concomitant medications in Section 8.4.

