The number and proportion of subjects with a $\geq 50\%$ decrease in sperm concentration at Week 26 (observed cases) will be presented by double-blind treatment group. The number of subjects who have a $\geq 50\%$ decrease in sperm concentration at any time up to Week 26 (to upper bound of analysis visit window) will be displayed to ensure that $\geq 50\%$ decreases from baseline in sperm concentration that fell outside of the analysis visit windows are accounted for.

CONTINUOUS ENDPOINTS	WHILE ON TREATMENT STRATEGY
Population	Semen Analysis Set (subjects with 2 evaluable semen samples collected at baseline and at the Week 13 analysis visit) as defined in Section 3.1.2 of this SAP.
Patient Level Outcome to be Measured	Change and Percentage Change from Baseline (continuous outcome) at Week 13. Outcome is determined based on the mean of 2 evaluable semen samples at a visit, and analysis visit windows are assigned based on first of 2 evaluable semen samples.
Measure of intervention effect and handling of intercurrent events	Measure of treatment effect assuming that the treatment effect prior to the intercurrent event of treatment early termination is of interest. Data included to last dose date double-blind drug + 7 days will be considered “while on-treatment” for those who permanently discontinue double-blind study drug.
Population level summary measure	Median Difference between treatment groups, comparing those assigned to filgotinib versus those assigned to placebo in the change and percentage change from baseline at Week 13 for a continuous outcome.
Estimators	
Main estimator: Quantile regression models will be used to estimate the median difference (filgotinib – placebo) in change and percentage change from baseline at Week 13, 95% CI for the sperm/semen parameter of interest. The CI=RANK option will be specified in PROC QUANTREG in SAS.
 
For sperm concentration (M/mL), the model will include: baseline sperm concentration (continuous).
 
For sperm total motility (%), percent normal morphology, total sperm count (M/ejaculate) and ejaculation volume (mL), the model will include: baseline value for parameter (continuous), and sperm concentration (15 – 50 M/mL, > 50 M/mL).

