6.5.2. Pre-Specified Sperm Decrease Threshold Criteria and Confirmed Semen Abnormalities

Subjects who met a pre-specified sperm decrease threshold criteria (a $\geq 50\%$ decrease in sperm concentration and/or motility and/or morphology) were to stop study drug and begin a standard of care regimen selected by the investigator in accordance with the protocol and be followed off study drug to evaluate for reversibility criteria.

A “confirmed semen abnormality” as defined by Jarvi and colleagues {Jarvi 2008} reflects the presence of abnormal sperm parameters potentially associated with decreased male fertility; the criterion is met when one or more of the following are observed: a sperm concentration < 5 M/mL, or sperm motility $< 20\%$, or a percent normal sperm morphology of $< 10\%$.

The number and proportion of subjects meeting any of the pre-specified sperm decrease thresholds (from the baseline value [mean of 2 evaluable semen collections at screening]) or any of the components of a confirmed semen abnormality (mean of 2 evaluable samples at a study visit) at the double-blind Week 13 (primary endpoint) visit will be displayed by double-blind treatment group:

Sperm Decrease Criteria

- $\geq 50\%$ decrease in sperm concentration
- $\geq 50\%$ decrease in sperm total motility
- $\geq 50\%$ decrease in sperm morphology [% normal] (WHO 1992 criteria)
- $\geq 50\%$ decrease in sperm concentration and ($\geq 50\%$ decrease in total motility and/or morphology [% normal] at the same visit)

Confirmed Semen Abnormality Criteria (as defined by Jarvi et al)

- Sperm concentration < 5 M/mL
- Sperm total motility $< 20\%$
- Sperm morphology (% normal) $< 10\%$
- Confirmed Semen Abnormality (Sperm concentration < 5 M/mL or sperm total motility $< 20\%$ or sperm morphology [% normal] $< 10\%$ at the same visit)

The number and proportion of subjects meeting any of the pre-specified sperm decrease thresholds or components of a confirmed semen abnormality (as described above) at the Week 26/OL Week 13 analysis visit and at/after the Week 39/OL Week 26 visit will be displayed by treatment sequence. Treatment sequences to be presented are:

- double-blind (DB) filgotinib
- DB filgotinib to open-label (OL) filgotinib
- DB placebo
- DB placebo to OL filgotinib

A listing of subjects who met any of the components of a confirmed semen abnormality will be provided.

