Descriptive statistics will be presented at Baseline, Week 26/OL Week 13, and subsequent visits by actual treatment sequence to explore the confounding effects of response to treatment. Study days will be used for assignment of analysis visit windows for subjects who stayed on randomized drug throughout study and for subjects who started on double-blind filgotinib and switched to open-label filgotinib. For subjects who switched from placebo to open-label filgotinib, days on open-label filgotinib will be used to assign analysis visit windows at/after Open-Label Week 13. Week 26 for the first 3 treatment sequences will be displayed along-side OL Week 13 for placebo to OL filgotinib group; Week 39 alongside OL Week 26 for placebo to OL filgotinib group, etc. to align with the originally planned study weeks; but using the at/after Protocol Amendment 3 visit schedule to ensure that subjects were on open-label filgotinib for an entire sperm cycle for the placebo to open-label filgotinib group.

A summary of the 4 hormone parameters and change and percentage change from baseline by visit will be presented for subjects with evaluable semen data at both baseline and ≥ 1 of the analysis visits at/after Week 26/OL Week 13. Shift tables from baseline to Week 26/OL Week 13 for LH, FSH, inhibin B, and total testosterone will be summarized by treatment sequence for the Week 26/Extension Phase Semen Analysis Set.

A by-subject listing will be provided for hormones. A separate listing of the hormone data for subjects who entered the Monitoring Phase of the study will be provided.

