Study Procedure	Screening 45 days	Part A (Section 6.4 Protocol)					Part B (Section 6.5 Protocol)		Open-Label Filgotinib Phase (Section 6.6 Protocol)					Long Term Extension (Section 6.10 Protocol)	30 Day Safety Follow-up ^e ±5 days	ET ^f	
		Day 1	Wk 2	Wk 4	Wk 8	Wk 13 ^a	Wk 20	Wk 26 ^a	Sperm Parameter Eligibility Confirmation ^b	OL Day 1	OL Wk 2	OL Wk 4	OL Wk 8	OL Wk 13 ^c			LTE Week 13 through LTE Week 195 ^d
			±5 days	±5 days	±5 days	+ 5 days	±5 days	+ 5 days			±5 days	±5 days	±5 days	+ 5 days			±10 days
Semen Collection (2 samples as per collection instructions in Protocol Section 6.13) ^a	X ^r					X	X	X ^s					X ^t	X		X	
Date and time of most recent ejaculation ^a	X					X	X	X					X	X		X	
HIV, Hepatitis B, and Hepatitis C ^v	X																
HBV DNA ^w					X		X						X	X			
Randomization		X															
Study Drug Accountability				X	X	X	X	X	X		X		X	X	X	X	
Study Drug Dispensation		X		X	X	X	X	X	X	X		X	X	X	X	X	
PK collection (sparse)			X ^x	X ^y		X ^z		X ^z			X ^x	X ^y		X ^z			
In-Clinic Dosing ^{aa}		X	X			X		X			X			X			

- a Weeks 13 and 26 must occur after 13 weeks and 26 weeks of drug exposure, respectively. Therefore, visit window for these visits are +5 days
- b Subjects on blinded study drug meeting criteria as a non-responder (Week 13) or for Disease Worsening (after Week 13 through 26), and not meeting the pre-specified decrease threshold in sperm parameters, are eligible for open-label filgotinib (refer to Appendix 11 and Section 3 of the protocol). For definitions of IBD response status, Disease Worsening, and/or pre-specified decrease threshold in sperm parameters please refer to Definition of Terms and Section 3.4 of the protocol.
- c OL Week 13 must occur after 13 weeks of starting open-label filgotinib. Therefore, visit window is +5 days.
- d Subjects in the LTE will undergo scheduled visits for safety assessments and semen sample collection every 13 weeks, starting with LTE Week 13. Semen monitoring will be collected until the Week 13 primary study results are analyzed.
- e Any time a subject discontinues study drug, a safety follow-up visit, 30 days (± 5 days) after the last dose of study drug is required, even if the subject is entering the Monitoring Phase

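### SAP 6.5.2 pools all semen visits from Week 39/OL Week 26 onward into one crude proportion per treatment sequence, so unequal numbers of later samples make the sequences non-comparable, and the denominator is not stated

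*SAP*

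**What the plan says.** SAP 6.5.2 lists four sperm-decrease criteria (concentration, motility, morphology, and concentration combined with either of the others) and the confirmed-abnormality criterion with its three components. After Week 13 it promises a number and proportion in two categories, the second of them open-ended: "at the Week 26/OL Week 13 analysis visit and at/after the Week 39/OL Week 26 visit will be displayed by treatment sequence". It gives no denominator for either category.

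The general rule is in SAP 3.2: "Semen and hormone data collected after Week 13 will be summarized by treatment sequence", and this is done "for subjects with baseline and ≥ 1 visit at/after Week 26". SAP 6.6.3 describes the hormone summary in the same way, "for subjects with evaluable semen data at both baseline and ≥ 1 of the analysis visits at/after Week 26/OL Week 13". Neither rule requires a sample at or after Week 39/OL Week 26.

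Other provisions bear on who is sampled and how often:

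- SAP Table 3-4 defines 13-weekly semen windows up to Week 221 and cuts on-treatment data at last dose plus 7 days.
- Under Protocol Section 3, non-responders at Week 26 or OL Week 13 stop drug, and LTE treatment ends at disease worsening. Under SAP 1.2, a man who meets a sperm threshold stops drug and enters the Monitoring Phase.
- SAP Appendix 1, footnote d, on the LTE: "Semen monitoring will be collected until the Week 13 primary study results are analyzed". That is a study-level date, so the number of LTE samples depends on when a man entered.

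**The concern.** A decrease can be seen only when an on-treatment semen pair is taken. A man with one later pair has one chance to meet a criterion; a man with six has six. A single proportion of men with any event ignores this. Time on drug after Week 26 depends on IBD response, so the number of looks can differ systematically between the four sequences. A difference between double-blind filgotinib and double-blind placebo, or between either and the open-label sequences, could then reflect follow-up alone.

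The missing denominator adds a second uncertainty. Under the SAP 3.2 population, a man whose last semen visit was Week 26/OL Week 13 is in the set but has no later sample. If he is counted, he can only count as event-free.

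Testicular safety is the purpose of the study, and for motility, morphology, the combined criterion and confirmed abnormality these are the only long-term proportions that the SAP describes. A reader will be inclined to compare them across sequences.

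**Working it through.** **Plan's own figures.** The plan gives no figure for this display. Its only sizing figure reproduces, 200/(1 − 0.20) = 250, and has no bearing on this point.

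**Inputs.** The windows come from SAP Table 3-4. The per-visit risk p, the number of later pairs k, the share f of the sequence with at least one later pair, and the within-man log-SD are assumptions, because the documents give none of them.

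**1. Number of looks.** Windows from Week 39 to Week 221: (221 − 39)/13 + 1 = 15. This is a ceiling; the stop to LTE semen collection makes actual numbers smaller and variable.

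**2. Any-event proportion among sampled men.** With constant, independent per-visit risk this is 1 − (1 − p)^k:

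| p | k = 1 | k = 2 | k = 4 | k = 8 | k = 15 |
|---|---|---|---|---|---|
| 2% | 2.0% | 4.0% | 7.8% | 14.9% | 26.1% |
| 5% | 5.0% | 9.8% | 18.5% | 33.7% | 53.7% |
| 8% | 8.0% | 15.4% | 28.4% | 48.7% | 71.4% |

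**3. Allowing for the shared baseline.** All later visits are compared with one baseline pair, so looks are correlated within a man. A simulation took log-normal sample values, the mean of two at each time, no drug effect, and men event-free at Weeks 13 and 26. The chance of at least one concentration decrease of 50% or more was:

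| log-SD | 1 pair | 2 pairs | 4 pairs | 8 pairs | ratio, 4 vs 2 |
|---|---|---|---|---|---|
| 0.35 | 1.8% | 3.4% | 6.1% | 10.3% | 6.1/3.4 = 1.8 |
| 0.45 | 4.2% | 7.7% | 13.2% | 21.0% | 13.2/7.7 = 1.7 |
| 0.55 | 6.5% | 11.7% | 19.4% | 29.7% | 19.4/11.7 = 1.7 |

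These figures are for concentration only. The documents give no variability for motility or morphology, but the mechanism is the same.

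**4. Effect of a wider denominator, if it is used.** The displayed figure becomes f × [1 − (1 − p)^k]. At p = 5% and k = 4, 18.5% becomes 14.8% (f = 0.8), 11.1% (f = 0.6) or 7.4% (f = 0.4).

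**5. Both effects together.** Take two sequences with the same 5% per-visit risk:

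- A, with f = 0.8 and k = 6: 0.8 × 26.5% = 21.2%.
- B, with f = 0.5 and k = 2: 0.5 × 9.8% = 4.9%.

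Restricted to sampled men they still show 26.5% and 9.8%, so correcting the denominator alone does not make them comparable. Over p = 2% to 8% the displayed pairs run from 9.1% versus 2.0% to 31.5% versus 7.7%.

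**6. Direction.** With f = 0.6, k = 6 and p = 5% the pooled figure is 0.6 × 26.5% = 15.9%, above the 5% single-visit risk. Repeated looks can outweigh the loss from unsampled men.

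**The case against.** The tempting stronger reading is that the SAP takes these proportions over everyone with a semen visit at or after Week 26, counts men never sampled again as event-free, and so understates the long-term rate. The documents do not establish that. Section 6.5.2 states no denominator, and SAP 3.2 says who enters the sequence summaries, not how an unsampled man is scored. Several provisions favour an observed-case reading:

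- SAP 3.5.1: "In general, missing data will not be imputed unless methods for handling missing data are specified".
- The neighbouring Week 26 display in SAP 6.2: "at Week 26 (observed cases) will be presented by double-blind treatment group".
- Where SAP 8.2.2.3, 8.2.3 and 8.5 state denominators, they leave out men without the relevant data.

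SAP 6.2 cites Section 3.1.2 for the Semen Analysis Set, and other sections name a Week 26/LTE semen set. The text of 3.1.2 was not available to me and may settle the matter. Dilution is therefore conditional, and nothing can be said about net direction.

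It would also be wrong to call this the only long-term summary. SAP 6.5.1 gives the concentration-decrease proportion by sequence and visit, and descriptive statistics for semen parameters at subsequent visits. SAP 6.6.2 reports reversibility by parameter and sequence for men who met a threshold in this period.

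Finally, the display is descriptive, with no test or interval. The sequences are post-randomisation groups, and SAP 6.5.1 itself speaks of confounding by IBD response. A person-time rate will not remove that confounding.

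All of this stands. It does not answer the unequal number of looks, which holds under either denominator. The observed-case label in SAP 6.2 belongs to a single-visit display. SAP 6.5.1 writes a sampled-in-window restriction for its summary of days on filgotinib; 6.5.2 writes none.

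**Conclusion.** The pooled rows from Week 39/OL Week 26 onward are not comparable between sequences, because they count any event over unequal numbers of on-treatment pairs without adjustment for visits or time. This follows from the design and does not depend on the denominator.

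The size rests on assumptions: about 1.7 to 1.8 times the apparent concentration-decrease rate for four later pairs rather than two, with no drug effect and log-SD between 0.35 and 0.55. A further reduction by the factor f applies only if men without a later sample are in the denominator, which 6.5.2 leaves open; f is unknown.

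The practical gap is mainly in motility, morphology, the combined criterion and confirmed abnormality, since concentration is already shown by visit. The Week 13 primary analysis, the secondary endpoints at Weeks 13 and 26, and the sample size are unaffected.

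**What to change.** In SAP 6.5.2, for the rows at and after Week 39/OL Week 26:

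1. Define the denominator as men with at least one evaluable on-treatment semen pair in that period.
2. Show the number of men and the number of evaluable pairs per sequence.
3. For every criterion, add either by-visit proportions, as SAP 6.5.1 already does for concentration, or a rate per 100 semen-observed patient-years with the exact Poisson interval of SAP 8.1.5.3. Time should end at the first event for that criterion or at the last evaluable on-treatment pair. It should not run to last dose plus 30 days or data cutoff, as it does for adverse events, because no decrease can be seen after the last pair.

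Step 1 alone is not enough, as the 26.5% versus 9.8% example shows. The cost is a few lines of SAP text and one extra table from data already collected. The table should carry a note that these are descriptive comparisons of post-randomisation sequences and remain confounded by IBD response.

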6.6. Exploratory Endpoints

6.6.1. Definition of the Exploratory Endpoints

The exploratory endpoints are:

- Percent of reversibility among subjects who experience a $\geq 50\%$ decrease in sperm concentration, and/or motility, and/or morphology
- Change from baseline in hormones, including LH, FSH, inhibin B, and total testosterone at Weeks 13 and 26

6.6.3. Hormones

Similar analysis methods used to summarize continuous secondary semen parameters will be used to analyze hormones LH, FSH, inhibin B, and total testosterone. Baseline will be the last value prior to administration of any study drug.

For all continuous hormone parameters, 8-point summary statistics (n, mean, SD, median, Q1, Q3, minimum, and maximum) by double-blind treatment group will be provided for the value at the visit, change from baseline, and percentage change from baseline in hormone parameter at Weeks 4 and 13 (change and percentage change values will be calculated from double-blind baseline). A 95% distribution-free CI on the median change and percentage change from baseline in all hormone parameters will be constructed by treatment at Week 4 and Week 13 using the

CIPCTLDF option in PROC UNIVARIATE in SAS. Quantile regression will be used to estimate the difference (filgotinib minus placebo) in median change and percentage change from baseline in hormones at double-blind Weeks 4 and 13 and to construct a 95% CI. The model will adjust for the baseline value of the hormone parameter as a continuous variable, and sperm concentration (15 - 50 M/mL, and > 50 M/mL). Since no subjects took concurrent MTX, and very few CD subjects were enrolled, these stratification factors will not be included in the model. The CI=RANK option will be specified in PROC QUANTREG in SAS.

Shift tables from baseline to Week 4 and Week 13 will be summarized by double-blind treatment group for the Semen Analysis Set for LH, FSH, inhibin B, and total testosterone. The shift tables include shift analysis for hormone parameters below, within, and above the central laboratory defined normal range for each specific hormone at baseline to below, within and above the normal range at Week 4 and Week 13.

Treatment-Sequence Hormone Displays for Week 26/OL Week 13 and Extension Phase

Descriptive statistics will be presented at Baseline, Week 26/OL Week 13, and subsequent visits by actual treatment sequence to explore the confounding effects of response to treatment. Study days will be used for assignment of analysis visit windows for subjects who stayed on randomized drug throughout study and for subjects who started on double-blind filgotinib and switched to open-label filgotinib. For subjects who switched from placebo to open-label filgotinib, days on open-label filgotinib will be used to assign analysis visit windows at/after Open-Label Week 13. Week 26 for the first 3 treatment sequences will be displayed along-side OL Week 13 for placebo to OL filgotinib group; Week 39 alongside OL Week 26 for placebo to OL filgotinib group, etc. to align with the originally planned study weeks; but using the at/after Protocol Amendment 3 visit schedule to ensure that subjects were on open-label filgotinib for an entire sperm cycle for the placebo to open-label filgotinib group.

A summary of the 4 hormone parameters and change and percentage change from baseline by visit will be presented for subjects with evaluable semen data at both baseline and ≥ 1 of the analysis visits at/after Week 26/OL Week 13. Shift tables from baseline to Week 26/OL Week 13 for LH, FSH, inhibin B, and total testosterone will be summarized by treatment sequence for the Week 26/Extension Phase Semen Analysis Set.

A by-subject listing will be provided for hormones. A separate listing of the hormone data for subjects who entered the Monitoring Phase of the study will be provided.

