6.2. Pretreatment Assessments

6.2.1. Screening Visit

Subjects will be screened within 45 days before randomization to determine eligibility for participation in the study. The 45 day Screening period may be extended in consultation with the medical monitor. Refer to the Study Procedure Tables in [Appendix 2](#) for a complete list of assessments to be performed and documented at Screening:

- Obtain written informed consent
- Obtain demographics and medical history (including onset of IBD, prior number of children fathered, disease characteristics, smoking habits, average weekly alcohol consumption, and family history of premature coronary heart disease)
- Review Inclusion / Exclusion Criteria
- Complete Physical Exam (PE) as detailed in [Appendix 7](#)
- Vital signs, weight and height
- Perform standard 12-Lead ECG

- QuantiFERON® test and Chest X-ray (CXR) (if applicable). QuantiFERON® positive or negative results must not be repeated. An indeterminate result should be repeated once and the second result (if positive or negative) will be accepted. Two sequential indeterminate results constitute a screen failure. Subjects with previously treated TB or newly identified latent TB during Screening require sponsor approval (See Inclusion Criterion No. 12 for details). Subjects who are diagnosed with latent TB at Screening must initiate an adequate course of prophylaxis according to local country guidelines for immunocompromised patients for a minimum of 4 weeks prior to randomization. Subject may initiate study drug dosing only after consultation with the medical monitor or designee. If a subject had a QuantiFERON® test for the purposes of clinical care or Screening for another Gilead-sponsored study within 60 days, the prior Gilead result may be used to assess eligibility with permission of the medical monitor or designee.
- Urinalysis, including a urine drug screen
- Obtain blood samples for:
 - Hematology and Serum Chemistry
 - Serology
 - Quantitative Ig subclasses
 - Endocrine tests: Thyroid stimulating hormone (TSH), HbA1c
 - Sex hormones, including LH, FSH, inhibin B, and total testosterone to be collected between 07:00 – 11:00 in the morning, if possible
- Stool Collection for:
 - *C. difficile* toxin, *E. coli*, *Salmonella spp*, *Shigella spp*, *Campylobacter spp* and *Yersinia spp* testing
 - Ova & Parasites (O&P)
- Review and collection of concomitant medications

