6.2.2. Day 1 Assessments

On Day 1, after the subject's eligibility for the study has been confirmed, the subject will be randomized into the study to receive filgotinib 200 mg or PTM filgotinib 200 mg once daily. Study drug will be dispensed as assigned by the IWRS system. The subject will take the first dose in clinic. Invasive study procedures such as blood draws should be done at the end of the Study Visit. The following will be performed and documented at Day 1 prior to dosing:

- Review Inclusion / Exclusion Criteria
- Symptom-driven physical examination, as needed
- Vital signs (resting blood pressure, respiratory rate, pulse and temperature)
- Weight (without shoes)
- Physician's Global Assessment [applied only to subjects with UC]
- Obtain blood samples for:
 - Hematology and Serum Chemistry
 - Lipid profile (fasting) [Total cholesterol and subfractions]
 - Sex hormones, including LH, FSH, inhibin B, and total Testosterone to be collected between 07:00 – 11:00 in the morning, if possible
- Urinalysis
- Review concomitant medications
- Record any adverse events related to protocol mandated procedures and all serious adverse events (SAEs) occurring after signing of the consent form.

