3.7. Analysis Visit Windows

3.7.1. Definition of Study Day

The First Dosing Date of Filgotinib/Placebo is defined as the date when subjects take their first dose of filgotinib/placebo, either double-blind or open-label drug, whichever is the earliest as recorded in the Study Drug Administration eCRF.

The Last Dosing Date of Filgotinib/Placebo is defined as the date when subjects take the last dose of filgotinib/placebo, either double-blind or open-label drug, whichever is later as recorded in the Study Drug Administration eCRF.

Study Day will be calculated from the first dosing date of double-blind filgotinib/placebo and derived as follows:

- For postdose study days: Assessment Date – On-Filgotinib/Placebo Study Day 1 + 1
- For days prior to the first dose: Assessment Date – Open-Filgotinib/Placebo Study Day 1

For subjects who are on placebo and switch to open-label filgotinib, the On-Filgotinib Study Day 1 is defined as the first dose date of open-label filgotinib.

Follow-up (FU) Day for subjects who discontinue study drug and/or enter the Monitoring Phase will be calculated from the last dosing date of any study drug, which is defined as the date when a subject takes their last dose of any study drug considering both double-blind and open-label drugs. The FU day is derived as Assessment Date – Last Dosing Date. Therefore, Follow-up Day 1 is the first day after permanent discontinuation of all study drugs.

Baseline is defined as the last available observation taken on or prior to the first dose date of double-blind filgotinib/placebo study drug.

Open-label Baseline is defined as the last available observation taken on or prior to the first dosing date of open-label filgotinib (used for safety assessments for placebo subjects who switch to open-label filgotinib with the exception of semen and hormone parameters). For semen parameters, including sperm concentration, total sperm count, ejaculate volume, sperm total motility, and sperm morphology, the baseline value is the mean of 2 evaluable samples from the screening visit. The baseline value for sperm/semen parameters is used to evaluate whether subjects have met pre-specified sperm parameter decrease thresholds (ie, $\geq 50\%$ decrease in sperm concentration and/or motility and/or morphology). For hormone parameters, the baseline value will be the last value on/prior to starting double-blind study drug, to be consistent with the rules that are used for sperm/semen data.

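### The hormone models adjust for only one of two pre-dose measurements; adding the Screening value as a second covariate would modestly sharpen the exploratory between-arm comparisons

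*SAP*

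**What the plan says.** The protocol schedules the same four hormones twice before treatment. Section 6.2.1 (Screening Visit) lists "Sex hormones, including LH, FSH, inhibin B, and total testosterone to be collected between" 07:00 and 11:00 if possible. Section 6.2.2 (Day 1 Assessments) lists them again for the same morning window, under the instruction "The following will be performed and documented at Day 1 prior to dosing". The procedures table in protocol Appendix 2 marks both visits.

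The SAP uses one of the two draws. Section 6.6.3 states: "Baseline will be the last value prior to administration of any study drug". Section 3.7.1 gives the same rule: "For hormone parameters, the baseline value will be the last value on/prior to starting double-blind study drug". The baseline window in SAP Table 3-3 is open-ended before Day 1, so both draws fall inside it, and the last one is taken. Section 6.6.3 then fits quantile regressions for the filgotinib-minus-placebo difference in median change and percentage change at Weeks 4 and 13. These adjust for the baseline hormone value and a two-level sperm-concentration stratum. The Screening hormone value does not enter the model.

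For semen, section 3.7.1 says "the baseline value is the mean of 2 evaluable samples from the screening visit".

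**The concern.** A single hormone draw is an imperfect reading of a man's usual level. A second pre-dose draw carries further information about that level, and hence about his value at Week 4 or 13 in the absence of a drug effect. Adjusting for one draw leaves more unexplained variation in the outcome than adjusting for both, so the interval on the treatment difference is wider than the data require.

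What is at stake is limited. The hormones support the interpretation of the semen results. Both documents class them as exploratory, and neither sets a power, precision target or decision rule for them. The loss is some interval width on four supporting comparisons. Randomisation protects the between-arm difference from bias under either approach.

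**Working it through.** **Figures in the plan.** The only sample-size figure that can be rebuilt is the enrolment target (SAP section 1.3): 200 / (1 − 0.20) = 250, which matches. No SD, effect size or within-man correlation is given for any hormone.

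**Assumptions.** Let ρ be the correlation between any two of a man's draws (Screening, Day 1, follow-up), with equal variances. The range 0.5 to 0.8 is assumed.

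**Residual variance after adjustment, as a fraction of the outcome variance.**

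- One pre-dose value: 1 − ρ²
- Both pre-dose values: 1 − 2ρ²/(1 + ρ)

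With equal correlations, entering the two values as separate covariates or as their mean gives the same second formula.

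| ρ | One value | Both values | Variance ratio | CI width ratio | 200 men worth |
|---|---|---|---|---|---|
| 0.5 | 0.750 | 0.667 | 0.889 | 0.943 | 225 |
| 0.6 | 0.640 | 0.550 | 0.859 | 0.927 | 233 |
| 0.7 | 0.510 | 0.424 | 0.830 | 0.911 | 241 |
| 0.8 | 0.360 | 0.289 | 0.803 | 0.896 | 249 |

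The variance falls by 11% to 20% and the interval narrows by 6% to 10%. At ρ = 0.3 the variance reduction is 5%; at 0.9 it is 22%.

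**Check in the SAP's type of model.** The formulas are for least squares. Simulated median regression of change on arm and baseline compared the two-draw mean with Day 1 alone (200 men, ρ of 0.5, 0.7 and 0.85, normal and log-normal data, with and without truncating Screening at ±2 SD). Variance ratios were about 0.77 to 0.92, with simulation noise of several points. That broadly agrees with the formulas.

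**If Screening predicts follow-up less well than Day 1.** Let s be the Screening-to-follow-up correlation and hold the other two at r. The residual variances are:

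- Mean of the two draws: 1 − (r + s)²/[2(1 + r)]
- Two covariates: 1 − (r² + s² − 2r²s)/(1 − r²)

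Dividing each by 1 − r², at r = 0.7:

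| s | Mean of two draws | Two covariates |
|---|---|---|
| 0.70 | 0.83 | 0.83 |
| 0.63 | 0.94 | 0.93 |
| 0.56 | 1.05 | 0.98 |
| 0.50 | 1.13 | 1.00 |

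The mean breaks even at s of about 0.59 and loses precision below that. The two-covariate model falls back to the Day 1-only variance, apart from the cost of one extra parameter.

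**The case against.** The strongest reply is that nothing here is wrong. The last pre-dose value is the SAP's general baseline rule, sections 3.7.1 and 6.6.3 agree on it, and no conclusion is shown to depend on it. That stands. This is an efficiency point about exploratory endpoints, and its size rests on an assumed correlation.

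A reader might go further and infer that baseline itself should become the mean of the two draws. The documents do not support that, for three reasons.

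- **Shift tables.** Post-baseline hormones are single draws, so a two-draw baseline has less spread than the value it is compared with. Take no drug effect, normal data, ρ = 0.7 and a lower limit at the 2.5th percentile (all assumed). With a single baseline, movement into and out of the low category is balanced at 1.67% each way. With a mean baseline it becomes 1.73% in and 0.91% out. The present rule is the better one for these tables, and a claim that it misclassifies men near a reference limit should not be made.
- **Selection.** Inclusion criterion 9 filters the Screening values. Averaging them into baseline would shift within-arm changes by about 0.01 to 0.07 SD, if the lowest 2% to 16% were excluded and ρ were 0.5 to 0.7. Both arms are affected alike, but section 6.6.3 also reports within-arm medians with intervals.
- **Timing.** Screening can be 45 days before randomisation, or more if extended. That makes a weaker Screening correlation plausible, and then a simple mean can lose precision.

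Nor does the semen rule set a precedent. Semen is sampled twice at every time point, so baseline and follow-up match. The remark in section 3.7.1 about consistency with the semen rules appears to concern double-blind versus open-label baseline, so it is not a contradiction. Finally, the 25% fall in variance from averaging two baselines, whatever the correlation, applies only to an unadjusted change score, which is not the planned comparison.

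**Conclusion.** The point holds as a minor one. The SAP's hormone models omit a pre-dose measurement that the trial already collects, and so forgo some precision in the between-arm comparisons at Weeks 4 and 13. With equally correlated draws and ρ of 0.5 to 0.8, the variance reduction forgone is about 11% to 20%, or an interval 6% to 10% narrower. The gain is smaller, down to nil, if Screening is a weaker predictor than Day 1. There is no bias and no error in the baseline definition. The documents support a second covariate; they do not support a new baseline.

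**What to change.** In SAP section 6.6.3, leave the last pre-dose value as baseline for change, percentage change, within-arm summaries and shift tables. Add the Screening value of the same hormone as a second continuous covariate beside it in the quantile-regression models.

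Two details need a sentence each: which Screening value counts after a permitted retest or rescreen (protocol sections 6.2.1 and 6.2.1.1), and what is entered when only one pre-dose value exists (for example, that value in both places).

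The SAP was signed in January 2021, and protocol amendment 6 describes the second interim analysis as already within the data monitoring committee's completed work. The model should therefore be reported beside the planned one and labelled as added; SAP section 1 already sends later changes to the clinical study report. Any pooled hormone analysis follows its own SAP (protocol section 8.12), which should be checked for alignment.

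The cost is one parameter per model and a short programming change. No new samples or visits are needed, and the descriptive tables do not change.
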